9.2.3 Handling of missing data in Continuous Endpoints

- **Mixed Model for Repeated Measures (MMRM):** The repeated measures analysis will be conducted using a mixed model including observed measurements at all visits. For the Placebo-Controlled Period, the mixed model includes the categorical fixed effects of treatment, visit and treatment-by-visit interaction, stratification factors at randomization [Baseline glucocorticoid (yes/no), number of prior failed b/tsDMARDs (1; 2 or more), and a combined prior anti-TNF failure/adalimumab use factor (prior anti-TNF failure with adalimumab use; prior anti-TNF failure without adalimumab use; no prior anti-TNF failure)], and the continuous fixed covariates of baseline measurement. For LTE periods, the mixed model includes the categorical fixed effects of treatment, visit and treatment-by-visit interaction, major stratum [baseline glucocorticoid use (yes/no) and prior adalimumab use (yes/no)], and the continuous fixed covariates of baseline measurement. An unstructured variance-covariance matrix (UN) will be used. If the model cannot converge, an appropriate covariance structure matrix (e.g., autoregressive (1) or compound symmetry) will be used. Parameter estimation is based on the assumption of data being missing at random and using the method of restricted maximum likelihood (REML).

MMRM will be the primary approach to the analysis of continuous variables

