7.4 Statistical Analyses for Efficacy

For the Placebo-Controlled Period, subjects will be analyzed according to the treatment group randomized. All statistical tests will be performed at a 2-sided significance level of 0.1. A 95% confidence interval of the treatment difference between each ABBV-154 dose and placebo will be provided.

- For categorical variables, a pairwise, comparison will be made between each ABBV-154 dose and placebo using the Cochran-Mantel-Haenszel (CMH) test, adjusting for the actual values of stratification factors. Non-Responder Imputation incorporating multiple imputation to handle COVID-19 (NRI-MI) will be the primary approach to handle missing data for categorical endpoints.
- For continuous variables, the comparison will be made between each ABBV-154 dose and placebo based on the MMRM adjusting for treatment, visit, interaction between treatment and visit, actual values of stratification factors as fixed factors, and BL value as a covariate. The MMRM will be the primary approach to handle missing values for continuous endpoints.

Through the Placebo-Controlled and Long-Term Extension Periods, descriptive statistics by treatment sequences will be provided at each visit. Categorical endpoints will be summarized by the number and proportion of subjects who achieved the endpoint, as well as the 95% confidence interval. Continuous endpoints will be summarized by descriptive statistics including mean, standard deviation, standard error, and the 95% confidence interval of the mean. In addition, continuous endpoints through Week 24 will be summarized using estimates from the MMRM by treatment sequence, visit, interaction between treatment sequence and visit, actual values of stratification as fixed factors and baseline values as a covariate.

Summary and Analysis of the Primary Endpoint

The primary endpoint is the achievement of ACR50 at Week 12. It will be evaluated using the ITT Population based on treatment as randomized. Comparison of the primary endpoint will be made between each ABBV-154 dose and placebo using the CMH test adjusting for the actual values of stratification factors. NRI-MI will be the primary approach to handle missing values. Analysis details for NRI-MI and other sensitivity analyses (if applicable) will be provided in the SAP.

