Activity	Screening Day -35 to Day -1	Baseline Day 1	D Day 4	Wk 2 Day 15	Wk 4 Day 29	Wk 6 Day 43	Wk 8 Day 57	Wk 10 Day 71	Wk 12 Day 85	Wk 14 Day 99	Wk 16 Day 113	Wk 18 Day 127	Wk 20 Day 141	Wk 22 Day 155	Wk 24 Day 169	Double-Blind LTE Period 1			LTE Period 2			PD Visit	30-D F/U Phone Call	70-D F/U Visit
																EOW Visits	EGW Visits	Wk 78	Wk 86	ESW Visits	Wk 182			
																EOW Visits	EGW Visits	Day 547	Day 603	ESW Visits	Day 1,275			
12-lead ECG	✓								✓						✓		Wk 36	✓		Wk 134	✓	✓		
Chest x-ray	✓																Wk 54 if applicable			Wk 110 and 166 if applicable				
DXA (Bone Density, Body Composition) Scan	✓													✓				✓		Wk 134	✓			
Physician's Global Assessment of Disease Activity		✓	✓	✓	✓		✓		✓	✓		✓		✓	✓		✓	✓	✓	✓	✓	✓		
TJC68 and SJC66	✓	✓	✓	✓	✓		✓		✓	✓		✓		✓	✓		✓	✓	✓	✓	✓	✓		
Erythrocyte sedimentation rate	✓																							

Activity	Screening	Baseline	D 4	Wk 2	Wk 4	Wk 6	Wk 8	Wk 10	Wk 12	Wk 14	Wk 16	Wk 18	Wk 20	Wk 22	Wk 24	Double-Blind LTE Period 1			LTE Period 2			PD Visit	30-D F/U Phone Call	70-D F/U Visit
	Day -35 to Day -1	Day 1	Day 4	Day 15	Day 29	Day 43	Day 57	Day 71	Day 85	Day 99	Day 113	Day 127	Day 141	Day 155	Day 169	EOW Visits	EGW Visits	Wk 78	Wk 86	ESW Visits	Wk 182			
Urine pregnancy test (for female of childbearing potential)		✓			✓		✓		✓		✓		✓		✓	Wk 28, 32, 40, 44, 52, 56, 64, 68, 76	Wk 36, 48, 60, 72	Wk 78, 82	✓	Wk 90, 94, 98, 102, 106, 110, 114, 118, 122, 126, 130, 134, 138, 142, 146, 150, 154, 158, 162, 166, 170, 174, 178		✓		✓
																								
Serum pregnancy test (females of child-bearing potential): FSH, if applicable	✓																							
hsCRP	✓	✓	✓	✓	✓		✓		✓	✓		✓		✓	✓		✓	✓	✓	✓	✓	✓	✓	
TSH	✓																							
Anti-citrullinated protein antibody	✓																							

Activity	Screening	Double-Blind LTE Period 1														LTE Period 2						30-D F/U Phone Call	70-D F/U Visit		
	Day -35 to Day -1	Baseline	D 4	Wk 2	Wk 4	Wk 6	Wk 8	Wk 10	Wk 12	Wk 14	Wk 16	Wk 18	Wk 20	Wk 22	Wk 24	EOW Visits	EGW Visits	Wk 78	Wk 86	ESW Visits	Wk 182			PD Visit	
	Day 1	Day 4	Day 15	Day 29	Day 43	Day 57	Day 71	Day 85	Day 99	Day 113	Day 127	Day 141	Day 155	Day 169	EOW Visits	EGW Visits	Day 547	Day 603	ESW Visits	Day 1,275					
Rheumatoid Factor	✓														✓			✓			✓				
Hematology	✓	✓		✓	✓		✓		✓	✓		✓			✓		✓	✓	✓	✓	✓	✓		✓	
HbA1c	✓	✓							✓						✓		Wk 36, 48, 60, 72			Wk 94, 118, 142, 166	✓			✓	
Clinical chemistry and urinalysis	✓	✓		✓	✓		✓		✓	✓		✓			✓		✓	✓	✓	✓	✓	✓		Clinical chemistry only	

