3.2 Secondary Endpoint(s)

All secondary endpoints are at Week 12.

- Change in Disease Activity Score (DAS) 28 (CRP) from Baseline;

- Change in Clinical Disease Activity Index (CDAI) from Baseline;
- Achievement of ACR20;
- Achievement of ACR70;
- Achievement of low disease activity (LDA) defined by DAS28 (CRP) ≤ 3.2 ;
- Achievement of LDA defined by CDAI ≤ 10 ;
- Achievement of clinical remission (CR) defined by DAS28 (CRP) < 2.6 ;
- Achievement of CR defined by CDAI ≤ 2.8 ;
- Change in the Health Assessment Questionnaire Disability Index (HAQ-DI) from Baseline.

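### The Placebo-Controlled Period MMRM imposes one baseline slope from Day 4 to Week 12, which may cost precision in the Week 12 contrasts for DAS28 (CRP), CDAI and HAQ-DI

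*SAP*

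**What the plan says.** SAP 9.2.3 makes this model the main method for continuous endpoints: "MMRM will be the primary approach to the analysis of continuous variables". All post-baseline visits are modelled jointly: "The repeated measures analysis will be conducted using a mixed model including observed measurements at all visits". Its fixed part up to Week 12 is set out thus: "the mixed model includes the categorical fixed effects of treatment, visit and treatment-by-visit interaction". Stratification factors come next, with baseline entering last: "and the continuous fixed covariates of baseline measurement". The covariance is left free: "An unstructured variance-covariance matrix (UN) will be used". Protocol 7.4 agrees, listing "actual values of stratification factors as fixed factors, and BL value as a covariate" beside treatment, visit and their interaction. Treatment-by-visit is the only interaction in either document.

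Three secondary endpoints in SAP 3.2 use this model: the Week 12 changes in DAS28 (CRP), CDAI and HAQ-DI. In the Activity Schedule (Protocol Appendix E), the joint counts ("TJC68 and SJC66"), both global assessments, hsCRP and HAQ-DI are all collected at Baseline, Day 4 and Weeks 2, 4, 8 and 12. Five post-baseline visits therefore share one baseline slope. SAP 9.4.3 plans no sensitivity analysis for the secondary endpoints.

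**The concern.** Day 4 is three days after the first dose. Scores should still sit close to baseline, so the regression of change on baseline should be shallow there. By Week 12 a steeper slope is plausible. Response is expected by then (SAP 2.4 assumes ACR50 in 13% on placebo and, with the 22-point difference, 35% on active), and entry requires at least six swollen and six tender joints at Baseline, which favours regression to the mean.

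The unstructured covariance does not repair this, because it describes residuals and the restriction is on the mean. The fitted slope is a weighted average that leans towards visits with small residual variance, usually the early ones. What is at stake is interval width for the Week 12 dose-versus-placebo differences, and how fully a chance baseline imbalance is removed from them.

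**Working it through.** **The plan's own figure.** SAP 2.4 claims at least 90% power for ACR50 with 85 per arm, 13% against 35%, two-sided alpha 0.1. The pooled rate is 0.24, so z = (0.22·√85 − 1.645·√(2·0.24·0.76)) / √(0.13·0.87 + 0.35·0.65) = (2.028 − 0.994)/0.584 = 1.77, giving 96.2%. The claim holds. It concerns the CMH endpoint, not this model. No power is stated for the continuous endpoints.

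**Formulas.** Let b be the vector of visit-specific slopes on baseline, and S the covariance of the visits given baseline. With unstructured covariance and one slope, the large-sample fitted slope is b_c = (1′S⁻¹b)/(1′S⁻¹1). Relative to visit-specific slopes, the Week 12 variance is multiplied by 1 + (b₁₂ − b_c)²·Var(baseline)/S₁₂,₁₂. This factor cannot fall below 1.

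**Inputs.** The documents supply the visits, the model terms and 85 per arm. Correlations with baseline and the ratio of Week 12 to baseline SD are assumptions.

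**Worked case: correlation 0.85 at Day 4, 0.5 at Week 12, equal SDs (baseline variance 1).**
- Raw-scale slopes at the five visits: 0.85, 0.74, 0.66, 0.56, 0.50.
- Under a first-order autoregressive pattern, with ρ = 0.85 and c the ratios of successive slopes, b_c reduces to [ρ/(1−ρ²)] / [ρ²/(1−ρ²) + 1 + Σ(1−c)/(1+c)].
- Numerator: 0.85/0.2775 = 3.063. Denominator: 2.604 + 1 + (0.069 + 0.057 + 0.082 + 0.057) = 3.869. So b_c = 0.792.
- On the change scale (subtract 1), the common slope is −0.21 against −0.50 at Week 12.
- Excess variance: (0.792 − 0.50)²/(1 − 0.25) = 0.114, or 11%. Standard error: √1.114, or +5.5%. Effective size: 85/1.114 = 76.3 per arm.
- A baseline imbalance between arms is under-corrected at Week 12 by 0.29 times its size.

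**Selected settings under the same pattern** (slopes on the change scale):

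| Correlation Day 4 / Week 12 | SD ratio | Week 12 slope | Common slope | Variance excess | SE excess | Effective n of 85 |
|---|---|---|---|---|---|---|
| 0.7 / 0.6 | 1.0 | −0.40 | −0.33 | 0.8% | 0.4% | 84.3 |
| 0.7 / 0.6 | 1.3 | −0.22 | −0.32 | 0.8% | 0.4% | 84.3 |
| 0.8 / 0.6 | 1.0 | −0.40 | −0.24 | 4.0% | 2.0% | 81.7 |
| 0.8 / 0.6 | 1.3 | −0.22 | −0.20 | 0.1% | 0.0% | 85.0 |
| 0.85 / 0.5 | 1.0 | −0.50 | −0.21 | 11.4% | 5.5% | 76.3 |
| 0.85 / 0.5 | 1.3 | −0.35 | −0.15 | 3.0% | 1.5% | 82.5 |
| 0.9 / 0.35 | 1.0 | −0.65 | −0.17 | 25.9% | 12.2% | 67.5 |
| 0.9 / 0.35 | 1.3 | −0.54 | −0.12 | 12.1% | 5.9% | 75.8 |

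In all, 28 settings were run: seven correlation pairs, two SD ratios and two residual patterns. The second pattern gave equal or slightly smaller excesses. In 22 of the 28 the SE excess is under 6%; the other six all combine equal SDs with a Week 12 correlation of 0.4 or less. Constant correlation with equal SDs gives no loss. A test with 90% power under visit-specific slopes would have 83 to 90% under the common slope.

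**Simulation** (five arms of 85, five visits, unstructured fit, 300 runs per setting). Variance ratios were 1.15, 1.09 and 1.03 against 1.114, 1.059 and 1.037 from the formula. With 7 to 8% dropout dependent on observed values they were 1.21, 1.04 and 1.07. Mean estimates lay between −0.49 and −0.51 under both models, where the truth was −0.50.

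**The case against.** The strongest reply is that a baseline main effect is already a valid covariate adjustment in a randomised trial, that the protocol and SAP agree with each other, and that nothing decisive hangs on this model. ACR50 is analysed by CMH, the sample size and the MCP-Mod analysis rest on ACR50, and the continuous endpoints carry no power claim and no multiplicity control. All of that stands, and it limits the point to efficiency.

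A reader might infer that the plan certainly under-adjusts all three endpoints by a known percentage each. The documents do not support this, because they give no SD, correlation or slope for any of them. With correlations 0.7 and 0.6 and SD ratio 1.3, the common slope slightly over-adjusts, at under 1% in variance. Even at 0.85 and 0.5 with equal SDs, other choices for the intermediate correlations and the residual pattern move the excess between about 7% and 21%. Variance percentages also look larger than their effect on interval width: 11% in variance is 5.5% in the standard error.

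A reader might also extend the point to the LTE models. The calculation covers only the five visits to Week 12, and no placebo arm continues after re-randomisation, so it gives no ground for changing them.

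**Conclusion.** The omission is plain in both documents, and the mechanism is sound: in large samples a common slope cannot beat visit-specific slopes at Week 12. A change in slope between Day 4 and Week 12 is plausible, but its size is not documented. On the assumed settings the cost is about 0 to 26% in Week 12 variance, or 0 to 12% in standard error and mostly under 6%. The case of 0.85 falling to 0.5 with equal SDs gives about 11%, or roughly 76 effective subjects of 85. These figures span the settings tried; they are not a bound.

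It would be wrong to read this as bias in the treatment effect. Randomisation protects the contrast, and the simulated means were essentially the same with and without the interaction. The primary analysis and sample size are unaffected. The change is still worth making: it costs almost nothing if slopes are equal and recovers precision if they are not.

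**What to change.** In SAP 9.2.3, add a baseline-by-visit interaction to the Placebo-Controlled Period MMRM, and align the model description in Protocol 7.4. With five post-baseline visits this adds four mean parameters, against about 425 subjects. The estimand, the Week 12 contrast and the data collected do not change. The term should be specified before unblinding for the Primary Analysis, since choosing it afterwards would be data-driven. The LTE model need not change on this ground.

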9.2.4 Summary of Long-Term Efficacy

Long-term efficacy in the LTE periods will be summarized using the As Observed case approach by treatment sequence (ABBV-154 40 mg EOW, ABBV-154 150 mg EOW, ABBV-154 340 mg EOW, ABBV-154 340 mg E4W, ABBV-154 150 mg EOW re-randomized from Placebo, ABBV-154 340 mg EOW re-randomized from Placebo).

- **As Observed (AO):** The AO analysis will be used for the summaries of long-term efficacy, which will not impute values for missing evaluations, and thus a

subject who does not have an evaluation on a scheduled visit will be excluded from the AO analysis for that visit.

- NRI-MI and MMRM will be used to summarize selected categorical and continuous efficacy variables, respectively, for long-term efficacy.

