5.3 Prohibited Medications and Therapy

In addition to the medications listed in the eligibility criteria, prior exposure to ABBV-154 or ABBV-3373 are NOT allowed. The following medications are prohibited through the end of study drug administration:

- All csDMARDs, except MTX;
- All tsDMARDs: Examples include but are not limited to the following: Xeljanz[®] (tofacitinib), Olumiant[®] (baricitinib), Rinvoq[®] (upadacitinib), Jyseleca[®] (filgotinib);
- All bDMARDs, including bio-originators and biosimilars. Examples include but are not limited to the following: Humira[®] (adalimumab), Enbrel[®] (etanercept), Remicade[®] (infliximab), Kineret[®] (anakinra), Rituxan[®] (rituximab), Cimzia[®] (certolizumab pegol), Simponi[®] (golimumab), Actemra[®] (tocilizumab), Raptiva[®] (efalizumab), Tysabri[®] (natalizumab), Stelara[®] (ustekinumab), Benlysta[®] (belimumab), Orencia[®] (abatacept);
- Through Week 24, oral glucocorticoids with the exception of prednisone ≤ 7.5 mg/d (or equivalent) at Baseline, which must be tapered to 0 within 4 weeks of Baseline unless a subject qualifies for rescue therapy as defined in Section 5.4;
- Any intra-articular, intramuscular, parenteral, trigger point or tender point, intra-bursa, or intra-tendon sheath glucocorticoid through Week 24 unless a subject qualified for rescue therapy defined in Section 5.4;
- Super high potency and high potency topical glucocorticoids;
- Any investigational drugs;
- Any live vaccination;
- Any opioid medications with exception of tramadol, combination of acetaminophen with codeine, or combination of acetaminophen with hydrocodone; and
- Any oral traditional Chinese medicine (e.g., tripterygium glycosides, sinomenine, total glucosides of white peony).

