5.4 Prior and Concomitant Therapy

Any medication or vaccine (including over-the-counter or prescription medicines, vitamins, and/or herbal supplements) that the subject is receiving at the time of enrollment or receives during the study must be recorded on the appropriate electronic case report form (eCRF) from 30 days prior to Baseline through the Post-Treatment Visit (70 day follow-up). Also, medications taken for RA since the date of diagnosis and any glucocorticoids (based on subject recollection and/or available medical records)

should be entered into the appropriate eCRF inclusive of the first and last dose, dosage, route of administration and reason for discontinuation, if known.

Subjects must remain on stable dose of MTX until Week 24 unless qualifying for rescue therapy as described below. A dietary supplement of oral folic acid (or equivalent, such as folinic acid) should be taken while the subject is taking MTX.

Through Week 24, NSAIDs and low potency analgesics (i.e., acetaminophen, tramadol, combination of acetaminophen with codeine, or combination of acetaminophen with hydrocodone) should continue to be used for the same reason and same dose each time but should not be taken within 24 hours prior to any study visit to avoid bias in outcome measurements.

At Week 18, rescue therapy should be offered to subjects classified as non-responders (defined as not achieving at least 20% improvement in either TJC or SJC at both Week 14 and Week 18) or after Week 18 for at least 2 consecutive visits as follows: 1) add or modify doses of MTX within the range of 7.5-25 mg/week, NSAIDs, acetaminophen/paracetamol, low potency opioid medications (tramadol or combination of acetaminophen and codeine or hydrocodone), oral glucocorticoids (up to maximum dose of prednisone 10 mg/day [or equivalent]) and/or 2) receive 1 intra-articular, trigger point or tender point, intra-bursa, or intra-tendon sheath glucocorticoids injection every 12 weeks.

At Week 30 and later, subjects classified as non-responders (defined as not achieving at least 20% improvement in either TJC or SJC at both Week 24 and Week 30, or after Week 30 for at least 2 consecutive visits) will discontinue study drug and initiate standard of care therapy at the investigator discretion (e.g., csDMARDs, b/tsDMARDs).

Methotrexate and oral glucocorticoids should be obtained locally as they will not be provided by AbbVie.

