5.6 Follow-Up After Subject Discontinuation of Study Drug or from Study

Discontinuation of Study Drug and Continuation of Study Participation

To minimize missing data for efficacy and safety assessments, subjects who prematurely discontinue study drug treatment should be encouraged to continue to be followed for all regularly scheduled visits as outlined in the [Appendix E](#), and adhere to all study procedures except for administration of study drug, annual TB testing, and PK sample collection, unless a subject decides to discontinue study participation entirely (withdrawal of informed consent). Subjects should continue to be advised on the scientific importance of their data even if they discontinue treatment with study drug early. Following the discontinuation of study drug, the subject should be treated in accordance with the investigator's best clinical judgment irrespective of whether the subject decides to continue participation in the study.

In addition, a 30-Day Follow-up Phone Call and a 70-Day Follow-up Visit after the last dose of study drug is required to ensure all treatment-emergent AEs/SAE have been resolved. All attempts must be made to determine the date of the last study drug dose and the primary reason for discontinuation of study drug or study participation. This information will be recorded on the appropriate eCRF page. This Follow-up Phone Call is not applicable for subjects who discontinue study drug prematurely and continue study participation with completion of at least 1 study visit at least 30 days after the last dose

of study drug. This Follow-up Visit is not applicable for subjects who discontinue study drug prematurely and continue study participation with completion of at least 1 study visit at least 70 days after the last dose of study drug.

Premature Discontinuation of Study (Withdrawal of Informed Consent)

If a subject prematurely discontinues study participation (withdrawal of informed consent), the procedures outlined for the Premature Discontinuation visit should be completed as soon as possible, preferably within 2 weeks, and preferably prior to initiation of another therapy.

For subjects to be considered lost to follow-up, reasonable attempts must be made to obtain information on the subject's final status. At a minimum, 2 telephone calls must be made, and 1 certified letter must be sent and documented in the subject's source documentation.

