9.2.2 Handling of missing data in Categorical Endpoints

- Non-Responder Imputation incorporating multiple imputation to handle COVID-19 and logistical problems (geo-political restrictions) (NRI-MI) will be the primary approach to handle missing data for categorical endpoints. The

NRI-MI will categorize any subject who does not have an evaluation during a pre-specified visit window (either due to missing assessment or due to early withdrawal from the study) as a non-responder for the visit. The only exceptions are: 1) when the subject is a responder both before and after the visit window, where the subject will be categorized as a responder for the visit, and 2) when the data is missing due to COVID-19 infection or logistical restriction, or logistical problems (geo-political restrictions), which will then be handled by Multiple Imputation. Subjects whose change/percent change from Baseline cannot be calculated because of a missing Baseline will be considered as a non-responder at all post-baseline visits in NRI-MI approach.

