9.5 Additional Efficacy Analyses

The primary and all secondary efficacy variables will be analyzed at all visits assessed other than Week 12, including in the LTE periods, using methods mentioned above. At time of the Primary Analysis, NRI will be used after Week 12 for all binary endpoints.

In addition, other efficacy endpoints described in Section 3.3 will be analyzed at all visits assessed using the same methods as secondary endpoints.

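### The planned long-term efficacy tables by ABBV-154 sequence keep values observed after study-drug stop or DMARD switch and do not separate them from on-drug response

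*SAP*

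**What the plan says.** **Analysis.** SAP 9.2.4 groups long-term efficacy by six ABBV-154 sequences, two of them re-randomized from placebo. The AO rule is: "The AO analysis will be used for the summaries of long-term efficacy, which will not impute values for missing evaluations". Its only exclusion is that a "subject who does not have an evaluation on a scheduled visit will be excluded from the AO analysis for that visit". The same section adds NRI-MI and MMRM for selected variables. SAP 9.5 carries the primary and secondary variables to other visits, "including in the LTE periods, using methods mentioned above".

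- NRI-MI (SAP 9.2.2): "NRI-MI will categorize any subject who does not have an evaluation during a pre-specified visit window" as a non-responder, with stated exceptions. Apart from a missing baseline, a missing evaluation is the only trigger.
- MMRM (SAP 9.2.3): "a mixed model including observed measurements at all visits".

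**Conduct.** Under Protocol 5.4, from Week 30, subjects meeting the non-responder definition "will discontinue study drug and initiate standard of care therapy at the investigator discretion (e.g., csDMARDs, b/tsDMARDs"). Protocol 5.3 limits the DMARD ban: "The following medications are prohibited through the end of study drug administration". Protocol 5.6 says that "subjects who prematurely discontinue study drug treatment should be encouraged to continue to be followed for all regularly scheduled visits".

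**Intercurrent events.** Protocol 7.3 and SAP 8.0 consider none for the primary and (key) secondary endpoints, which SAP 3.1 and 3.2 define at Week 12. No separate rule is given for the extension periods.

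**The concern.** Taken together, these provisions mean that a subject whom the protocol has classed as a non-responder to ABBV-154, and who then responds to another csDMARD or b/tsDMARD, is tabulated as a responder in an ABBV-154 sequence. This follows from the definitions; the SAP never says in words that such values are kept.

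A reader of the extension table could not tell how much of the response at a visit was on study drug. Protocol 7.1 says that analyses after the primary one may inform the Phase 3 design, so these summaries may be used beyond description.

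The other planned tables do not close the gap. SAP 5.0 counts study-drug discontinuations by period, and SAP 7.3 summarises DMARD use, but neither is linked to efficacy values at a visit. SAP 7.3 also leaves out medications started more than 70 days after the last dose, so a later switch is missing even there.

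**Working it through.** **Step 1: does any extension method remove values after a stop or switch?**

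- AO: drops a subject only when there is no evaluation. An observed post-switch value stays.
- NRI-MI: acts on missing evaluations or a missing baseline. An observed post-switch value stays.
- MMRM: uses all observed measurements. An observed post-switch value stays.

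None of the three conditions on being on study drug.

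**Step 2: when can such values arise?** The mandated stop with permitted switch starts at Week 30. The first affected six-weekly visits are Weeks 36, 42, 48, 54, 60, 66, 72 and 78 (eight visits). Stops for other reasons (Protocol 5.5) can produce off-drug values earlier. LTE Period 2 is offered to those who completed Period 1, and the protocol does not define completion, so carry-over beyond Week 78 cannot be settled.

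**Step 3: the plan's own figure.** The plan gives no rate for the extension. The nearest figures are the sample-size inputs in Protocol 7.10: placebo ACR50 13%, difference 22 points, about 85 per group, two-sided 0.1.

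- Pooled rate 0.24; null SE = √(2·0.24·0.76/85) = 0.0655.
- Alternative SE = √((0.13·0.87 + 0.35·0.65)/85) = 0.0633.
- Power = Φ((0.22 − 1.645·0.0655)/0.0633) = 96.2%, consistent with the stated minimum of 90%.

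The point does not depend on this power; only the 13% and 35% rates are borrowed below.

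**Step 4: illustration.** All inputs are assumptions.

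- R = 0.13 + 0.22 = 0.35: share of all ITT subjects in a sequence who respond on study drug. This is a Week 12 planning rate, held fixed whatever the share stopped.
- s = 0.10 to 0.30: share stopped, all non-responders on drug.
- q = 0.13 to 0.35: response to the next therapy, bounded by the two planning rates.
- f = 1 or 0.5: share of stoppers still attending. Everyone on drug attends.

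Formulas:

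- AO = (R + s·f·q)/(1 − s + s·f)
- NRI-MI = R + s·f·q
- Stoppers counted as non-responders = R
- On-drug only = R/(1 − s)

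| s, q | AO and NRI-MI, f=1 | AO, f=0.5 | NRI-MI, f=0.5 | Stoppers as non-responders | On-drug only |
|---|---|---|---|---|---|
| 10%, 13% | 36.3% | 0.3565/0.95 = 37.5% | 35.65% | 35% | 38.9% |
| 20%, 24% | 39.8% | 0.374/0.90 = 41.6% | 37.40% | 35% | 43.75% |
| 30%, 35% | 45.5% | 0.4025/0.85 = 47.4% | 40.25% | 35% | 50.0% |

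**Step 5: differences.**

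- Against stoppers as non-responders, full attendance: s·q = +1.3 to +10.5 points (midpoint +4.8).
- The same at half attendance: AO +2.5 to +12.4 (midpoint +6.6), NRI-MI +0.65 to +5.25 (midpoint +2.4). Lower attendance widens the AO gap, because absent stoppers leave its denominator, and halves the NRI-MI gap.
- Against on-drug only, full attendance: s·(q − R/(1 − s)), from −0.4 (s=10%, q=35%) to −11.1 (s=30%, q=13%), midpoint −4.0. It turns positive only if q exceeds R/(1 − s).

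**The case against.** The strongest reply is that using every observed value is a deliberate and legitimate choice. The rationale in Protocol Appendix F for removing confounding-medication handling gives two reasons. One is that such medication is prohibited through the placebo-controlled period or kept at a stable dose, which does not cover the time after a Week 30 stop. The other is comparability with earlier trials that did not use that handling, which has no time limit. The entry covers all endpoints. This stands: a reader might infer an oversight, but the documents do not show one, and the AO table should be kept. What is missing is a statement of what the table contains and a way to see the on-drug part.

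A reader might also infer that the two kinds of response can never be told apart. That goes too far. Protocol 5.6 has the last-dose date recorded on the eCRF, and Protocol 5.4 has medications recorded. The planned tables lack the split; the data do not. Table shells are not among the documents, so a clarifying footnote may exist there.

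Finally, the consequence is limited. Protocol 7.4 makes the extension summaries descriptive and specifies the by-sequence MMRM only through Week 24; it is the SAP that extends MMRM further. This also stands, and it keeps the point at the level of a reporting improvement.

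**Conclusion.** The point holds as a statement about the planned tables. AO, NRI-MI and MMRM all keep values observed after study-drug discontinuation, including after a DMARD switch, and report them under the ABBV-154 sequence. The reading of the text is firm; the size is not. The documents give no stopping rate, attendance rate or response to later therapy, so the ranges above rest wholly on assumed inputs.

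Two stronger readings are tempting and are not supported:

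- That the extension rates are inflated in favour of ABBV-154. On the same inputs AO lies above the rate that counts stoppers as non-responders and below the on-drug-only rate. The documents name neither as the reference, and the direction of any effect on differences between doses cannot be derived.
- That the Week 12 results are compromised. The mandated stop and switch begins at Week 30, so it does not reach the Week 12 primary and secondary analyses or MCP-Mod. Earlier stops for other reasons may leave some off-drug values before then, but for those endpoints the plan states that no intercurrent events are considered.

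The change should be made, but no confirmatory conclusion depends on it.

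**What to change.** In SAP 9.2.4:

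1. Keep the AO summary and state that it includes values after study-drug discontinuation or a switch to another csDMARD or b/tsDMARD.
2. Show, per visit and sequence, the number evaluated and the number still on study drug.
3. For binary extension endpoints (at least ACR50 and the variables selected for NRI-MI), add a companion summary on the full ITT denominator of each sequence. It counts subjects as non-responders from study-drug discontinuation or start of another csDMARD or b/tsDMARD, with NRI-MI for other missing data. For the two placebo-origin sequences, the denominator is those re-randomized at Week 12.
4. Optionally, for continuous endpoints, add an MMRM with those values set to missing and state its missing-at-random assumption.

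The cost is SAP wording, one flag built from dosing and medication dates, and a few extra tables. Because other DMARDs are prohibited while on study drug, the last-dose date alone identifies the off-drug values of subjects who follow the protocol. The companion rates will be somewhat lower than AO. The optional MMRM would estimate what happens had stoppers continued, which is a different question. No clinical rule changes.
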